7.5.1.14 Weeks 49 and afterwards

Patients will self-administer INC424 BID as instructed, morning and evening (at approximately 12-hour intervals), in an outpatient setting. Patients will call the investigator or designated research staff if they experience any unexpected and unfavorable signs and/or symptoms.

7.5.1.15 Weeks 60 (\pm 7 days) and each 12 Weeks thereafter (Week 72, 84, 96, etc)

The following procedures will be performed and all observations will be recorded in the eCRF:

- Review of concomitant medications.
- Update transfusion history status.

- A targeted physical examination will be performed, including body weight and measurement of spleen by palpation ([Section 8.2.3](#)).
- Vital signs (blood pressure, heart rate, respiratory rate and body temperature) to be performed in a sitting position after 5 minutes of rest.
- Blood sampling for serum chemistry tests, hematology, and optional coagulation (PT, PTT, or INR) (see [Appendix III](#)).
- Determination of ECOG performance status (see [Appendix IV](#)).
- Record adverse events.
- Document new (changed) OR ongoing dose information for INC424. Dose changes that are necessary between study visits will be communicated immediately and directly to the patient by telephone; the communication will be documented in the source documents.
- INC424 for the next 84 days (plus overage) will be dispensed along with dosing instructions.
- Drug accountability assessment (see [Section 6.5.4](#))
- Assess patient compliance.
- Patients will be instructed to call the investigator or designated research staff if they experience any unexpected and unfavorable signs and/or symptoms. Patients will be reminded to bring the study drug to the clinic with them.

7.5.1.16 Missed/moved visit

If a visit is moved or missed, the next scheduled visit should comply as much as possible with the original schedule.

7.6 End of treatment visit, including premature withdrawal and study discontinuation visit

Patients who discontinue study treatment before the end of the study should be scheduled for a visit as soon as possible, at which time all of the assessments listed for the End of Treatment (EOT) visit will be performed. The appropriate eCRF page should be completed, giving the date and reason for stopping the study treatment. At a minimum, all patients who discontinue study treatment, including those who refuse to return for a final visit, will be contacted for safety evaluations during the 28 days following the last dose of study treatment.

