included diarrhea (5.9%), fatigue (4.3%), headache (3.3%), peripheral edema (2.6%), pain in extremities (2.6%), urinary tract infections (2.6%), dizziness (2.6%), dyspnea (2.6%), asthenia (2%), fever (2%), cardiac murmur (2%), musculoskeletal pain (2%), peripheral neuropathy (2%), edema (2%), anxiety (2%), insomnia (2%), epistaxis (2%), flatulence (2%), and nausea (2%). The majority of these were Grade 1/2 CTCAE toxicity. Grade 3/4 nonhematologic toxicity included fatigue (1.3%), asthenia (2%), fever (0.7%), anxiety (1.3%) and insomnia (1.3%). Hematologic toxicity consisted primarily of anemia and thrombocytopenia. Thrombocytopenia appeared to be dose related occurring less frequently in the 15 mg BID group (3% Grade 3) than the 25 mg BID group (23% Grade 3; 6% Grade 4). Thrombocytopenia was not related to JAK V617F mutational status. Grade 3 thrombocytopenia occurred in 10% of patients receiving 10 mg BID of INC424, 3% of patients receiving 15 mg BID of INC424, 23% of patients receiving 25 mg BID of INC424, 60% of patients receiving 50 mg BID of INC424, 0% of patients receiving 25 mg QD of INC424, 27% of patients receiving 50 mg QD of INC424; 33% of patients receiving 100 mg QD; and 0% of patients receiving 200 mg QD of INC424. Thrombocytopenia of Grade 4 severity occurred in 0% of patients receiving 10 mg BID of INC424, 0% of patients receiving 15 mg BID of INC424, 6% of patients receiving 25 mg BID of INC424, 20% of patients receiving 50 mg BID of INC424, 0% of patients receiving 25 mg QD of INC424, 9% of patients receiving 50 mg QD of INC424, 0% of patients receiving 100 mg QD of INC424, and 33% of patients receiving 200 mg QD of INC424. Thrombocytopenia occurred more frequently in patients with lower baseline platelet counts (< 200 x 10⁹/L), and was reversible within 1 to 3 weeks after dose interruption and/or reduction. New onset anemia occurring in patients who were not transfusion dependent at baseline occurred in 23% of patients across all dosing intervals, and was most common in the 25 mg BID dosing cohort (27%) and least common in the 15 mg BID dosing cohort (8%). Anemia, though dose dependent, largely reflects the low Hgb status at baseline in this disease population.

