3.3 Study endpoints

3.3.1 Safety

- Safety and tolerability will be collected by monitoring the frequency, duration and severity of all grade AEs by the National Cancer Institute CTCAE v. 3.0, performing physical exams (PE), and evaluating changes in vital signs (VS), ECOG performance status (PS), electrocardiograms (ECGs) and serum chemistry, hematology results.
- Grade 3 and 4 AEs, Serious Adverse Events (SAEs).
- Change in laboratory values from Baseline to End of Treatment (serum chemistry and hematology).
- Changes in weight from Baseline to each assessment point and at end of treatment.
- Cardiac function as assessed by electrocardiograms (ECGs).

- Changes in vital signs.

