6.2.5 Optional dose tapering strategy in the event of study drug discontinuation

Following interruption or discontinuation of ruxolitinib, symptoms of myelofibrosis may return over a period of approximately one week. There have been cases of patients discontinuing ruxolitinib who sustained more severe events, particularly in the presence of acute intercurrent illness. It has not been established whether abrupt discontinuation of ruxolitinib contributed to these events. Unless abrupt discontinuation is required, gradual tapering of the dose of ruxolitinib may be considered, although the utility of the tapering is unproven.

When a decision is made to permanently discontinue INC424 therapy for reasons other than low platelet counts or ANC levels, a dose tapering strategy may be considered, based on evaluation of the condition of the patient, current dosing regimen, and the clinical judgment of the investigator. If considered to be medically necessary, the investigator may use any treatment to manage withdrawal from INC424 including a gradual tapering of the study drug dosage or use of other medications to manage adverse drug reactions of discontinuation. Short-term courses of corticosteroids have been used to moderate the withdrawal of INC424 and may be considered as part of a tapering strategy. Corticosteroids may be started prior to, or concurrent with, INC424 tapering. When a decision has been made to discontinue the patient with utilization of a tapering strategy, regardless of the use of concomitant medications, safety data will continue to be assessed in accordance with the protocol until the end of INC424 administration and in the event of an AE through resolution of the AE.

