7.6.1 Criteria for premature withdrawal

Patients may voluntarily withdraw from the study at any time without penalty of jeopardizing their health care or loss of benefits to which the patient is otherwise entitled or be dropped from it at the discretion of the investigator at any time. Every reasonable effort should be made to determine the reason a patient withdraws prematurely and this information should be recorded in the eCRF. A patient may be withdrawn from the study if, in the investigator's medical judgment, the patient is non-compliant with the study requirements. A patient **MUST** be withdrawn from the study if she becomes pregnant, or if he intends to father a child during the anticipated duration of study participation. The investigator **MUST** discontinue a patient from the study if the following occurs:

[figure not shown]
[REDACTED]

- Consent is withdrawn.
- Further participation would be injurious to the patient's health or well-being in the investigator's medical judgment.
- The study is terminated.
- If the study drug has been interrupted for 8 weeks or more for any reason, except in the case of splenectomy where a maximum of 12 weeks of drug interruption is permitted.
- The study drug has been permanently discontinued for safety according to the criteria specified in [Section 6.2.6](#). Specifically:
 - **Hematologic toxicity.** The lowest allowed dose (5 mg BID or 5 mg QD with concomitant CYP3A4 inhibitor or those patients with low platelet counts [50,000 – <100,000/ μ L]) is not tolerated due to the following:
 - Platelets cannot be maintained \geq 50,000/ μ L.
 - Absolute neutrophil count cannot be maintained \geq 500/ μ L.
 - Hemoglobin cannot be maintained \geq 6.5g/dL despite the use of transfusion therapy (or if the patient will not accept blood transfusions).
 - **Non-hematologic toxicity.** The lowest allowed dose (5 mg BID or 5 mg QD with concomitant CYP3A4 inhibitor or those patients with low platelet counts [50,000 – <100,000/ μ L]) is not tolerated due to the following:
 - The occurrence of a Grade 4 laboratory abnormality that is considered at least possibly related to the study drug, and is clinically significant in the view of the investigator. Exceptions NOT requiring study withdrawal are serum iron, total bilirubin not accompanied by direct bilirubin of 2 x ULN, triglycerides, total cholesterol, HDL cholesterol, not accompanied by at least a Grade 3 elevation of serum creatinine.

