 - Recurrence of a Grade 4 clinical event (non-laboratory based) after re-challenge with the study drug. Exceptions NOT requiring study withdrawal are fatigue, insomnia, obesity, constitutional symptoms (disabling but not life threatening), salivary gland changes, arthritis, and joint effusion.

Study drug MAY be permanently discontinued for a Grade 4 clinical event that has NOT been confirmed upon rechallenge with the study drug, at the option of the investigator.

If a patient is withdrawn from the study:

- The study Medical Monitors (Sponsor and CRO) must be notified.
- The reasons for discontinuation must be documented in the patient's medical record and eCRF.
- The End of Treatment Visit procedures should be completed at the last study visit while patient is receiving INC424 study drug.
- The Follow-up Visit should be performed 28 to 37 days after the last dose of study drug was taken (i.e., 28 - 37 days after the End of Study Visit).

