7.6.2 End of treatment evaluations

7.6.2.1 End of study or early termination visit

The End of Study or Early Termination Visit constitutes the final study visit where study drug has been taken. An End of Study Visit may occur with a planned discontinuation for any reason (e.g., at Week 20, it is determined that patient will participate in the study only 1 more month; therefore, the Week 24 Visit will become the End of Study Visit).

The following procedures will be performed and all observations will be recorded in the eCRF:

- Review of concomitant medications.
- Update transfusion history status.
- A targeted physical examination will be performed, including body weight and measurement of spleen by palpation ([Section 8.2.3](#)).
- Vital signs (blood pressure, heart rate, respiratory rate and body temperature) to be performed in a sitting position after 5 minutes of rest.
- Blood sampling for serum chemistry tests, hematology (see [Appendix III](#)).
- Determination of ECOG performance status (see [Appendix IV](#)).
- Drug accountability assessment (see [Section 6.5.4](#)).
- Record adverse events.
- Document the dose the patient was on at the time of study discontinuation.
- Patients will be asked to return to the clinic between 28 and 37 days later for a final Follow-up Visit.
- The sponsor (Novartis Pharmaceuticals) will be notified of the patient withdrawal.

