$\leq -50\%$, (-50%, -25%], (-25%, -5%], (-5%, 5%], (5%, 25%], (25%, 50%] and $\geq 50\%$

The descriptive summary will include the mean, standard deviation, median, minimum, maximum and 95% CI of the mean over time and at EOT visit for patients who were palpable at baseline and remained palpable or non-palpable at the post-baseline visit considered. In addition, number (n) of patients who remain non palpable, or became palpable from non-palpable at baseline will also be displayed.

WBC and platelet count changes from Baseline at end of each visit/month of therapy and at end of treatment. For each parameter, the percent of change will be computed by dividing the difference of value at assessment time and at baseline by the value at baseline, and multiplying by one hundred. WBC and platelet count changes from baseline will be summarized at end of each visit of therapy and at end of treatment.

Shift in fibrosis in the bone marrow from Baseline, is defined as the status change of fibrosis at time of worst/best response (whenever it occur) compared to fibrosis status at baseline.

Assessment of fibrosis in the bone marrow after enrollment is not mandatory and a listing will be provided with the results of the bone marrow biopsy (if performed).

Progression free survival (PFS) is the time from first study drug administration to date of documented progression (based on International Working Group for Myelofibrosis Research and Treatment Response Criteria) or deaths. Time will be censored at the last date the patient is known to be free of disease progression for patients without event. Deaths on or before the follow up/study completion evaluation visit (on-treatment and post-treatment deaths – Section 3.4.1.2) will be considered in the analyses.

Leukemia free survival (LFS) is the duration from first study drug administration to date of documented leukemia. Observation will be censored, if leukemia is not observed before the

end-of-study, death or lost to follow-up, at last date the patient is known to be free of leukemia. Deaths on or before the follow up/study completion evaluation visit (on-treatment and post-treatment deaths – Section 3.4.1.2) will be considered in the analyses.

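### The protocol times the End of Treatment assessments both on drug and after drug has stopped, and the SAP's end-of-treatment summaries set no drug-status rule, so those rows can mix the two

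*Protocol*

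**What the plan says.** On when the EOT assessments take place, the protocol points two ways.

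- After drug has stopped. Section 7.6: "Patients who discontinue study treatment before the end of the study should be scheduled for a visit as soon as possible", and the EOT assessments are done at that visit. Section 6.2.6 asks sites to bring patients who have permanently stopped back for the same evaluations.
- On drug. Section 7.6.1: "The End of Treatment Visit procedures should be completed at the last study visit while patient is receiving INC424 study drug". Section 7.6.2.1: "The End of Study or Early Termination Visit constitutes the final study visit where study drug has been taken". Section 7.5 (repeated in SAP 1.1) turns a visit at which drug is stopped that day into the End of Study Visit.

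The term itself has two definitions. Section 4.1 equates end of treatment with the day of the last dose. The glossary takes the later of the final evaluation visit and the stopping of drug.

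One mandatory withdrawal criterion in 7.6.1 reads "If the study drug has been interrupted for 8 weeks or more for any reason", with up to 12 weeks allowed for splenectomy.

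SAP 3.4.3 summarises change in spleen length with the "95% CI of the mean over time and at EOT visit for patients who were palpable at baseline", and WBC and platelet change at end of treatment. Protocol 3.3.1 lists as a safety endpoint: "Change in laboratory values from Baseline to End of Treatment (serum chemistry and hematology".

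**The concern.** An end-of-treatment row is normally read as the patient's state at the end of exposure. Here the drug status behind each value depends on how the patient stopped. Someone who stops at a planned visit is measured on drug. Someone who stops between visits is measured off drug under 7.6, after an interval the protocol does not limit. The mix therefore need not be random, because it can follow the reason for leaving.

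The protocol's own background gives reason to expect that off-drug values can differ. Section 1.3.4.1 says thrombocytopenia in the phase I/II study "was reversible within 1 to 3 weeks after dose interruption and/or reduction". Section 6.2.5 says that after interruption or discontinuation "symptoms of myelofibrosis may return over a period of approximately one week". If the EOT rows pool both states without saying so, they describe neither the end of exposure nor a defined time after it.

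**Working it through.** The plan gives no figure to reproduce: the study is descriptive, with no sample size or power calculation (Protocol 11.8, SAP 3.9). The check is a comparison of passages plus some date arithmetic.

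**1. Can the timing statements hold together?**
- Patient stops at a scheduled visit: 7.5, 7.6.1 and 7.6.2.1 agree. Time off drug is 0 days, and 7.6 adds nothing.
- Patient stops between visits, or is withdrawn during an interruption: 7.6 and 6.2.6 call for a visit after the last dose. Sections 7.6.1 and 7.6.2.1 point to a visit that has already passed. Both cannot be followed.

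**2. How far off drug can an EOT value be?**
- Withdrawal under the interruption rule: 8 weeks × 7 = 56 days or more since the last dose.
- Splenectomy exception: 12 weeks × 7 = 84 days. This case bears on counts and laboratory values only, since there is no spleen left to measure.
- Section 7.6 sets no upper limit.

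**3. Does the SAP select by drug status?**
- Section 2.3 treats every assessment after baseline as post-baseline and includes the 28 days after stopping.
- Section 3.4.4.2 uses all scheduled and unscheduled assessments unless stated otherwise.
- Last-dose rules exist for exposure (3.2) and for classifying deaths (3.4.1.2). None is applied to the EOT spleen or count summaries in 3.4.3.
- Section 3.5 cuts safety reporting at the end-of-treatment date plus 28 days, without saying which definition of that date applies.

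**4. What do the two definitions do to that cut-off?** Take a laboratory value at a visit 56 days after the last dose.
- Protocol 4.1 definition: the cut-off is day 28, so the value lies 56 − 28 = 28 days outside.
- Glossary definition: end of treatment is day 56 and the cut-off is day 56 + 28 = 84, so the same value is inside.

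Either way, the cut-off admits four weeks off drug, which is longer than the 1 to 3 weeks quoted for platelets.

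**5. How large is the effect?** Write f for the share of EOT values taken off drug and d for the mean difference between an off-drug value and the on-drug value the same patients would have shown. The EOT mean shifts by f × d. The documents give neither f nor d, and the sign of d is not established either. No bias figure can be stated.

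**6. What does not depend on the EOT row?**
- The primary analysis counts treatment-emergent adverse events, including by definition those in the 28 days after the last dose (Protocol 11.5.1, SAP 3.4.1.1).
- Spleen reduction of at least 50% is assessed at any time, and best overall response over the whole follow-up (SAP 3.4.3).
- The laboratory tables in SAP 3.5.2 use the worst post-baseline grade.

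**The case against.** The strongest reply is that the intent is clear enough: an EOT visit at or close to the last dose. Section 7.6.1 counts the follow-up window of 28 to 37 days from the last dose and from the End of Study Visit as if they were the same date. Section 4.1 uses the last-dose day, 7.6 asks for speed, and off-drug status has its own Follow-up Visit in 7.6.3.1. The study tests no hypothesis, and patients leaving at study end or commercial availability can have a planned final visit.

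This holds as a reading of intent and limits the reach of the point. It does not cover patients who stop between visits or are withdrawn during a long interruption, for whom a visit at the last dose is no longer possible. The SAP still pools their values with the rest.

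Three stronger readings are tempting, and the documents do not support them.

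- A reader might infer that EOT platelet counts hide toxicity because held patients have recovered by then. But Table 6-4 and 6.2.3.2 permit restarting once platelets reach 50,000/µL, and 6.2.2.2 provides for withdrawal where the count does not improve. Patients held for platelets to the 8-week limit may often be those who did not recover. The quoted reversal time also covers dose reduction, not only interruption. Worst-grade tables keep the nadir, and a laboratory abnormality that requires a change in study treatment is itself an adverse event (9.1.1, 9.1.2.1).
- A reader might infer that the EOT spleen mean is pulled toward baseline by a calculable amount. Section 6.2.5 concerns symptoms, and the documents give no rate of spleen regrowth off drug.
- A reader might take the SAP to summarise all laboratory values at EOT. Section 3.5.2 summarises change by study visit and worst grade. Only spleen length, WBC and platelets carry explicit end-of-treatment summaries there; the general laboratory change to EOT is a protocol endpoint.

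**Conclusion.** The contradiction is in the current text, and the SAP does not resolve it. Followed as written, the plan allows the EOT rows for spleen length, WBC and platelets, and the protocol's laboratory change-to-EOT endpoint, to combine values from 0 days to 56 days or more off drug. Whether they will do so to an important degree is unknown: the share of off-drug EOT values and their difference from on-drug values are not given, so neither size nor direction can be claimed.

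The reach is limited to these EOT summaries. The primary safety analysis and the main response summaries stand. The point is worth acting on because the affected rows cannot be interpreted without a drug-status rule and the remedy is small.

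**What to change.** In the protocol, reconcile 7.6 and 6.2.6 with 7.5, 7.6.1 and 7.6.2.1, so that the EOT assessments have one stated timing relative to the last dose. Reconcile the definitions of end of treatment in 4.1 and the glossary, and have SAP 3.5 name the one behind its 28-day cut-off.

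In SAP 3.4.3, and for the laboratory endpoint in Protocol 3.3.1, use the last-dose date from the EOT page to report two things separately:

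- the last post-baseline value on or before the last dose;
- EOT values taken after the last dose.

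For both, show the distribution of days between last dose and assessment.

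The cost is one derivation and some wording. Visit observations go into the eCRF, and SAP 3.2 already takes the last-dose date from the EOT page, with imputation rules where it is missing. No dosing or stopping rule changes. The downside is that the last on-drug value can be up to about 12 weeks old in patients who stop between 12-weekly visits, which the reported interval makes visible.

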7.6.1 Criteria for premature withdrawal

Patients may voluntarily withdraw from the study at any time without penalty of jeopardizing their health care or loss of benefits to which the patient is otherwise entitled or be dropped from it at the discretion of the investigator at any time. Every reasonable effort should be made to determine the reason a patient withdraws prematurely and this information should be recorded in the eCRF. A patient may be withdrawn from the study if, in the investigator's medical judgment, the patient is non-compliant with the study requirements. A patient **MUST** be withdrawn from the study if she becomes pregnant, or if he intends to father a child during the anticipated duration of study participation. The investigator **MUST** discontinue a patient from the study if the following occurs:

[figure not shown]
[REDACTED]

- Consent is withdrawn.
- Further participation would be injurious to the patient's health or well-being in the investigator's medical judgment.
- The study is terminated.
- If the study drug has been interrupted for 8 weeks or more for any reason, except in the case of splenectomy where a maximum of 12 weeks of drug interruption is permitted.
- The study drug has been permanently discontinued for safety according to the criteria specified in [Section 6.2.6](#). Specifically:
 - **Hematologic toxicity.** The lowest allowed dose (5 mg BID or 5 mg QD with concomitant CYP3A4 inhibitor or those patients with low platelet counts [50,000 – <100,000/ μ L]) is not tolerated due to the following:
 - Platelets cannot be maintained \geq 50,000/ μ L.
 - Absolute neutrophil count cannot be maintained \geq 500/ μ L.
 - Hemoglobin cannot be maintained \geq 6.5g/dL despite the use of transfusion therapy (or if the patient will not accept blood transfusions).
 - **Non-hematologic toxicity.** The lowest allowed dose (5 mg BID or 5 mg QD with concomitant CYP3A4 inhibitor or those patients with low platelet counts [50,000 – <100,000/ μ L]) is not tolerated due to the following:
 - The occurrence of a Grade 4 laboratory abnormality that is considered at least possibly related to the study drug, and is clinically significant in the view of the investigator. Exceptions NOT requiring study withdrawal are serum iron, total bilirubin not accompanied by direct bilirubin of 2 x ULN, triglycerides, total cholesterol, HDL cholesterol, not accompanied by at least a Grade 3 elevation of serum creatinine.
 - Recurrence of a Grade 4 clinical event (non-laboratory based) after re-challenge with the study drug. Exceptions NOT requiring study withdrawal are fatigue, insomnia, obesity, constitutional symptoms (disabling but not life threatening), salivary gland changes, arthritis, and joint effusion.

Study drug MAY be permanently discontinued for a Grade 4 clinical event that has NOT been confirmed upon rechallenge with the study drug, at the option of the investigator.

If a patient is withdrawn from the study:

- The study Medical Monitors (Sponsor and CRO) must be notified.
- The reasons for discontinuation must be documented in the patient's medical record and eCRF.
- The End of Treatment Visit procedures should be completed at the last study visit while patient is receiving INC424 study drug.
- The Follow-up Visit should be performed 28 to 37 days after the last dose of study drug was taken (i.e., 28 - 37 days after the End of Study Visit).

